7.3 Subject Population(s) for Analysis

All subjects enrolled in the study who completed at least 4 food diaries per week during the diet modification phase will be used for analysis.

8 Safety and Adverse Events

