Specific Aim 1: In a clinical trial, will investigate the ability of CR to modulate the effects of radiation in the treatment of early breast cancer. Aim 1a. Adherence will be assessed and is defined for each patient as achieving 25% reduction of her normal caloric intake (weekly average of diet journals), during at least 80% of the days during the intervention. Aim 1b. Acute skin toxicity as defined by the National Cancer Institute Common Toxicity Criteria (NCI CTCv.4 for skin reaction, pain and the occurrence of moist desquamation) will be followed to ensure noninferiority as compared with historical controls. **Specific Aim 2: Investigate measurable changes of patient characteristics along with serum markers from CR to determine a metric for evaluating this treatment in future studies.** Patient characteristics such as weight, vital signs, body fat measurements, psychosocial evaluation and outcomes will be monitored. Additionally, members of the IGF-1R-AKT pathway, and glucose and insulin in the serum, will be assessed to create a molecular signature of response to this therapy.

The innovative use of caloric restriction as a novel therapeutic option has the potential to change the biology of tumors and enhance the clinical benefit of current treatments for breast cancer. If patients are noted to be compliant, we will be able to open a larger study to determine if the combination of radiation and caloric restriction is more efficacious than radiation alone.

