3.2 Primary Study Endpoints

Objective: Investigate the feasibility of a clinical trial administering ionizing radiation with concurrent CR for the treatment of breast cancer. True adherence will be defined as a successful reduction of 25% of total calories based on diet journals in at least 80% of the logged events. Acute skin toxicity as defined by the National Cancer Institute Common Toxicity Criteria (NCI CTCv.4 for skin reaction, pain and the occurrence of moist desquamation) will be followed to ensure noninferiority as compared with historical controls.

To obtain baseline caloric intake, patients will keep food diaries for 7 to 10 days. On the basis of these diaries, a caloric intake will be computed for each day. Each patient's baseline (pre-diet) caloric intake will then be the average caloric intake in this pre-diet phase. The target caloric intake during the diet phase will be set to 75% of this baseline average (25% restriction).

The diet phase will be defined as the entire length that a patient is on the calorically restricted diet. This includes a minimum of 2 weeks before the patient starts radiation therapy and a minimum of 2 weeks after completion of radiation therapy. This will guarantee that patients have been on the diet for a minimum of 10 weeks, regardless of whether or not the patients have exceeded the 10 weeks. In the diet phase, patients will also keep daily food diaries. An average daily caloric intake will be computed for each week. If that daily average is more than the restricted target or if there are fewer than 4 diaries during any given week, that week will be considered as non-adherent. Overall adherence with the diet intervention over the entire study will be defined as at least 80% of all logged events meeting the diet restriction target.

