4.5.2 Data Collection and Follow-up for Withdrawn Subjects

According to FDA regulations, when a subject withdraws from the study, the data collected on the subject to the point of withdrawal remains part of the study database and may not be removed.

A subject who is withdrawing needs to state whether he/she wishes to provide continued follow-up and further data collection subsequent to withdrawal from the interventional portion of the study.

If a subject withdraws from the interventional portion of the study, but agrees to continued follow-up of associated clinical outcome information as described in the previous bullet, the subject will continue follow up visit and evaluation per the protocol.

If a subject withdraws from the interventional portion of a study and does not consent to continued follow-up of associated clinical outcome information, study data related to the subject collected prior to the subject's withdrawal from the study will included in the study analysis. However, the subject's clinical data will not be used for dose escalation determination.

5 Study Drug/Therapy

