7 STATISTICAL PLAN

7.1 Sample Size Determination

The study will enroll a total of 90 patients. For Phase 1, with a sample size of 40, the study has 83% power to establish that adherence is higher than 60%, assuming that true adherence will be 80% or greater (one-sided exact binomial test with alpha 0.05).

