7.2 Statistical Methods

Primary endpoint (adherence). We will compute the proportion of patients who are adherent to the diet restriction (as defined in section 3.2), along with a 95% exact confidence interval. We will also use an exact binomial test (with a one-sided alpha of 0.05) to test whether adherence is greater than 60%.

Aim 1b. We will compute the proportion of patients with toxicity, along with a 95% exact confidence interval. Our institution's historical toxicity rate among similar patients is about 80% and we aim to prove that the dietary intervention is non-inferior with an absolute margin of 10%, using an exact binomial test. With a total sample size of 90 and assuming that true toxicity will be 80% or lower, we have 82% power (with one-sided alpha of 0.05).

Secondary endpoints. The change in body fat measurement between baseline and the end of the study will be analyzed via a paired t-test. Weight changes over time will be assessed by modeling BMI as a function of time (baseline, diet weeks 1, 3, 5, 7, and 10) via mixed-effects regression. The patterns of change over time in vital signs, insulin and other clinical labs, serum markers, and psycho-social outcomes (FACT-B) will also be analyzed similarly. If some of these measures are skewed, we will transform them (e.g., log) before the analyses. Finally, local recurrence, distant metastases, progression free survival, and overall survival will be analyzed via survival methods, specifically the Kaplan-Meier method and the logrank test. If sufficient events occur, we may assess the impact of various patient and clinical/treatment variables on these outcomes via Cox proportional hazards regression.

Local recurrence, progression free survival, distant metastases and overall survival will be assessed and compared with historic controls using the Kaplan Meier method. Local recurrence, progression free survival, distant metastases and overall survival will be measured from the date of study enrollment to time of event.

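### Section 7.3 analyses only patients with at least 4 diaries per week, although section 3.2 scores sparse diary weeks as non-adherent, so one exclusion can turn a failed adherence test into a success

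*Combined protocol and SAP*

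**What the plan says.** - **Endpoint (3.2).** A week fails if average daily intake exceeds the target, and also "if there are fewer than 4 diaries during any given week, that week will be considered as non-adherent". A patient is adherent if at least 80% of logged events meet the target. On duration: "The diet phase will be defined as the entire length that a patient is on the calorically restricted diet".
- **Test (7.2).** "We will compute the proportion of patients who are adherent to the diet restriction (as defined in section 3.2"), followed by a one-sided exact binomial test at 0.05 "to test whether adherence is greater than 60" percent. No denominator is given.
- **Population (7.3).** "All subjects enrolled in the study who completed at least 4 food diaries per week during the diet modification phase will be used for analysis". This is the only population statement. It exempts no endpoint, and it does not say whether the count applies to every week or on average.
- **Withdrawals (4.5.2).** For a patient who withdraws and declines follow-up, "study data related to the subject collected prior to the subject's withdrawal from the study will included in the study analysis".
- **Sample size (7.1).** "with a sample size of 40, the study has 83% power to establish that adherence is higher than 60" percent, if the true rate is at least 80%. The corresponding toxicity statement in 7.2 uses all 90 patients. Neither allows for exclusions.
- **Use of the result (1.2).** "If patients are noted to be compliant, we will be able to open a larger study".

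**The concern.** Sections 3.2 and 7.3 apply the same diary threshold in opposite directions. Under 3.2 too few diaries count against the patient. Under 7.3 too few diaries remove her from the analysis. Of the two ways to fail a week, only one leads out of the denominator.

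Neither reading of 7.3 avoids this. If it means every week, no analysed patient can have a sparse week and the rule in 3.2 never operates. If it means on average, the patients who leave are the chronically sparse loggers, whom 3.2 would most clearly fail.

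When excluded patients are less adherent than the rest, the adherence estimate is too high and the 5% level may be lost. Phase 2 of this trial has no adherence gate, but section 1.2 rests the case for a larger study on compliance, so a false success would carry forward.

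The same diary filter also defines the population for the Aim 1b skin toxicity test, although toxicity is assessed at clinic visits and does not depend on diaries. Whether patients withdrawn for toxicity are analysed is unclear: 7.3 may drop them, while 4.5.2 keeps the data collected before withdrawal.

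**Working it through.** **1. Reproduce the plan's figures.** Inputs from 7.1 and 7.2: n = 40, null 0.60, alternative 0.80, one-sided 0.05, exact binomial.
- P(X ≥ 29 | 40, 0.60) = 0.0709 and P(X ≥ 30 | 40, 0.60) = 0.0352, so success needs at least 30/40.
- Power = P(X ≥ 30 | 40, 0.80) = 0.839, against 83% stated.
- Toxicity: n = 90, null 0.80 + 0.10 = 0.90. P(X ≤ 75 | 90, 0.90) = 0.0333, so non-inferiority needs at most 75/90. Power = P(X ≤ 75 | 90, 0.80) = 0.821, against 82% stated.

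**2. Results that change when patients are removed.** Adherence p-value = P(X ≥ x | n, 0.60).

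| All patients | p | After exclusion | p | Change |
|---|---|---|---|---|
| 29/40 | 0.071 | 29/39 (1 non-adherent out) | 0.045 | fail to success |
| 28/40 | 0.129 | 28/37 (3 non-adherent out) | 0.035 | fail to success |
| 30/40 | 0.035 | 28/38 (2 adherent out) | 0.057 | success to fail |

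The last row can occur under the every-week reading. Taking the week as the unit and 10 diet weeks, a patient with one or two sparse weeks can still meet the target in 8 of 10 (80%), so she is adherent under 3.2 yet excluded by 7.3.

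**3. False-success rate when true adherence among all patients is 0.60.** The documents give neither the excluded share e nor the adherent share q among the excluded, so both are assumptions. The number analysed is m ~ Binomial(40, 1 − e). The rate in the analysed set is (0.60 − e·q)/(1 − e); for example, e = 0.10 and q = 0 gives 0.60/0.90 = 0.667. The critical value is recomputed for each m and the result is averaged over m.

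| q | e = 5% | 10% | 15% | 20% | 25% |
|---|---|---|---|---|---|
| 0 | 8.0% | 15.9% | 29.3% | 48.5% | 70.9% |
| 0.2 | 6.2% | 10.2% | 16.3% | 25.3% | 37.6% |
| 0.4 | 4.8% | 6.1% | 8.0% | 10.5% | 13.6% |
| 0.6 (unrelated) | 3.6% | 3.5% | 3.5% | 3.4% | 3.3% |
| 0.8 | 2.7% | 1.9% | 1.3% | 0.9% | 0.5% |

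**4. Toxicity.** The same model with N = 90, a true rate of 0.90, and every excluded patient having had toxicity (worst case) gives false non-inferiority of 3.6%, 5.2%, 7.4% and 13.9% at 2%, 5%, 10% and 20% excluded, against 3.3% with no exclusions. If exclusion is unrelated to toxicity, the figure stays at 3.1–3.6%. A result of 76/90 fails (p = 0.063). It takes four exclusions of patients with toxicity to pass: 73/87 gives p = 0.05004 and 72/86 gives p = 0.046.

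**5. Power if loss is unrelated to outcome (true rate 0.80).** At 10% loss, power is 79.5% for adherence and 79.2% for toxicity. At 20% loss it is 74.1% and 74.7%.

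**The case against.** - **The text of 7.3 is softer than an exclusion rule.** It does not contain the word only, and 4.5.2 keeps data from withdrawn patients. That leaves toxicity withdrawals unclear. It does not supply another denominator for adherence, because no other population is defined.
- **The average reading is kinder.** Patients with a few sparse weeks would stay and be scored by 3.2. This narrows the problem, but those still dropped are the ones 3.2 would fail.
- **The large error rates need extreme inputs.** The 49% and 71% figures need 20–25% excluded with none of them adherent, and these conditions pull against each other. The every-week reading excludes more patients but catches some adherent ones. The average reading excludes mostly non-adherent patients but fewer of them. If 40% of the excluded are adherent, the 5% level is passed only modestly (6.1% at 10% excluded). The one-patient flip also needs a result next to the cut-off. All of this stands, and the less extreme rows are the better guide to size.
- **The unit of adherence is itself unsettled.** Section 3.2 scores weeks but then counts logged events, and Aim 1a in 1.2 speaks of days. If unlogged time is not a logged event, changing 7.3 alone would not close the gap. This stands as a reason to name the unit in the same amendment.
- **Toxicity is a lesser matter.** This is correct: the effect is small unless exclusions are both frequent and strongly linked to toxicity.

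**Conclusion.** The concern holds and must be fixed. As written, the plan makes entry to the primary analysis depend on a component of the primary endpoint, and no all-patient or sensitivity analysis is specified. That one exclusion can reverse the primary conclusion is exact arithmetic and needs no assumption about rates, only a result of 29/40 and a non-adherent patient removed.

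The size of the error in general rests on assumed e and q. With 10% excluded, false success is 6–16% when at most 40% of the excluded are adherent. There is no inflation if exclusion is unrelated to adherence, and the test is conservative if the excluded are more adherent than the rest. Because 3.2 itself scores sparse weeks as failures, independence is hard to assume. Even without bias, exclusions take power below the stated 83% and 82%. The effect on toxicity is secondary and depends on how 7.3 and 4.5.2 are reconciled.

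**What to change.** Replace 7.3 with one population per endpoint.

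- **Adherence:** all enrolled patients who start the diet. Each diet week with fewer than 4 diaries counts as non-adherent, as in 3.2. State that the 80% threshold is a share of weeks, and align 1.2, 2.1, 3.2 and 5.6 with it. Report separately how many patients enrolled but never started the diet.
- **Weeks after withdrawal:** section 3.2 is silent on these. Add a rule that planned diet weeks after withdrawal count as non-adherent. This is a new and conservative choice and should be presented as such.
- **Toxicity:** all patients who start the diet and receive at least one radiation fraction, whatever their diary count. Include all events up to withdrawal, and later events where follow-up is consented, consistent with 4.5.2.
- **Sensitivity analysis only:** the diary-completer set, with a statement of whether it means at least 4 diaries in every week or on average.

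The cost is protocol and SAP wording, with no new data and no change to sample size. The adherence estimate may come out less favourable.

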4.5 Early Withdrawal of Subjects

4.5.1 When and How to Withdraw Subjects

Patients will be informed that they have the right to withdraw from the study at any time for any reason, without prejudice to their medical care. The investigator also has the right to withdraw patients from the study for any of the following reasons:

1. Intercurrent illness
2. Occurrence of an unacceptable adverse event such as a Grade ≥ 4 toxicity or $\geq 20\%$ weight
3. Missing more than 3 consecutive days of planned radiation
4. Patient request
5. Protocol violations based on the judgment of PI
6. Non-compliance
7. Administrative reasons
8. Failure to return for follow-up
9. General or specific changes in the patient's condition unacceptable for further treatment in the judgment of the investigator
10. Patients may withdraw from the study voluntarily at any time; however, the Principal Investigator reserves the right to remove patients from the study for any of the following reasons.
11. Radiation toxicity becomes too severe and the patient can no longer tolerate consecutive radiation treatments as determined by treating radiation oncologist.
12. Patients are hospitalized for another condition that is unrelated to breast cancer. Particularly admissions lasting longer than 4 days.
13. Patients develop any of the exclusionary conditions during treatments including: hepatic insufficiency, diabetes, disorders requiring corticosteroid treatment, renal failure or pregnancy.
14. Patients become sexually active and do not wish to use contraception or patients discontinue previous method of contraception and remain sexually active.

At the time of withdrawal, all study procedures outlined for the End of Study visit should be completed. The primary reason for a patient's withdrawal from the study is to be recorded in the source documents.

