5.1 Description

Baseline caloric intake will be assessed by food diaries for 7 to 10 days prior to radiation treatment planning. Recommendations by nutritional counseling will be made to decrease total caloric intake by 25% and the patient will begin this diet immediately after the planning session and for a minimum of 2 weeks before starting radiation. The patient will then remain on this calorically restricted diet as measured by food diaries until completion of radiation treatment and for a minimum of 2 weeks after the completion of the radiation course. This is done to ensure that he patients undergo caloric restriction for a minimum of 10 weeks +/-1-2 weeks.

Restriction of calories is the primary objective of dietary modification and will be tailored to each patient by the discretion of the recommending physician in Integrative Medicine to ensure overall nutrition. Diet guidelines and compliance will be reviewed at weekly on-treatment visits by study staff including physicians and diet counselors.

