5.5 Preparation and Administration of Study Drug/Therapy

Patients will be expected to keep food diaries for 7 to 10 days prior to radiation treatment planning in order to calculate each patient's appropriate calorie intake during the treatment period. Initially, patients will have a consultation with integrative medicine and they will meet weekly with research staff for nutritional guidance and behavioral counseling to maintain their dietary modification. Patients will be expected to record their dietary intake on a daily basis while on treatment and these food journals will be collected weekly and modifications will be suggested accordingly. Patients will ultimately be responsible for modifying their diet as recommended to them.

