5.6 Compliance Monitoring

Adherence to dietary modification will be monitored by self-reported calorie intake in food journals that will be collected on a weekly basis. Patients will be expected to complete food diaries accurately to represent the type and quantity of food they consumed. Patients who have internet access at home and are comfortable with computers will be given the option of using an online food diary that is password protected, but viewable by the study staff. Should patients select this option, they will be assigned a username and create their own password.

The mean weekly caloric intake will be measured and adherence will be compared with their baseline evaluation. Patients will have to maintain a weekly 25% reduction of caloric intake for 80% of the logged events in order to be considered compliant for this trial.

See Appendix IX for printed food diary and access to online food diary.

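### Sections 7.3 and 3.2 treat under-logged weeks differently, leaving the Phase 1 adherence denominator and the scoring of early leavers open

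*Combined protocol and SAP*

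**What the plan says.** Section 7.3 defines one population for all analyses: "All subjects enrolled in the study who completed at least 4 food diaries per week during the diet modification phase will be used for analysis". It makes no exception for adherence.

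Section 3.2 handles the same shortfall week by week: "if there are fewer than 4 diaries during any given week, that week will be considered as non-adherent". The patient stays in and is adherent overall if at least 80% of logged events meet the target. The same section sets the period: "The diet phase will be defined as the entire length that a patient is on the calorically restricted diet", with an intended minimum of 10 weeks. Section 5.1 is looser about length, aiming to "ensure that he patients undergo caloric restriction for a minimum of 10 weeks +/-1-2 weeks".

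On withdrawal, 4.5.2 says of a patient who declines further follow-up that "study data related to the subject collected prior to the subject's withdrawal from the study will included in the study analysis". It does not say how she is scored for adherence.

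Section 7.2 refers to 3.2 for the definition of adherence but names no denominator. Section 7.1 powers the test on 40 patients (60% against 80%, one-sided exact binomial, alpha 0.05, power 83%) and allows for no exclusions.

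**The concern.** Keeping a diary is part of the behaviour that Phase 1 tests, and 3.2 recognises this by counting a short week as a failure. If 7.3 means every week, no analysed patient can have a short week, so the 3.2 rule has nothing to act on. The primary feasibility endpoint is then conditioned on part of its own outcome.

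The alternative is to let the diet phase end when the patient leaves the diet. That keeps more patients in but opens a different gap: a patient who leaves after a few good weeks has no later weeks to fail.

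Two analysts could choose differently and reach opposite Phase 1 conclusions from the same data. Section 1.1 makes successful caloric restriction the basis for opening a larger study.

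**Working it through.** **Inputs.** From 7.1: n = 40, null 60%, alternative 80%, one-sided exact test at 0.05. Loss rates are assumptions, because the documents give none.

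**1. The plan's own figure.** The required count is the smallest r with P(X ≥ r | 40, 0.6) ≤ 0.05. P(X ≥ 29) = 0.0709 and P(X ≥ 30) = 0.0352, so r = 30. Power is P(X ≥ 30 | 40, 0.8) = 0.839, which agrees with the stated 83%.

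**2. One patient.** With 29 adherent of 40, p = 0.071 and the test fails. Remove one non-adherent patient: 29 of 39 gives p = 0.045 and the test passes.

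**3. The rules applied to single patients, taking weeks as the logged events.**
- Eight of 10 weeks on target and two under-logged: 8/10 = 80%, adherent under 3.2, but excluded by a strict 7.3.
- Three clean weeks, then quits: 3/3 = 100%, adherent if the diet phase ends with her; 3/10 = 30%, non-adherent over 10 planned weeks.

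**4. First reading: non-adherent patients leave the denominator.** Let A ~ Bin(40, 0.6) be the adherent patients and W ~ Bin(40 − A, f) the non-adherent patients lost. Success means that A reaches the exact 5% critical count for n = 40 − W. On average 40 × 0.4 = 16 patients are non-adherent, so f = 5% or 10% means 0.8 or 1.6 patients lost.

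**5. Second reading: would-be non-adherent patients quit early with clean diaries and score adherent.** All 40 stay in, and the chance of scoring adherent becomes 0.6 + 0.4f. False success is P(X ≥ 30 | 40, 0.6 + 0.4f). For example, f = 5% gives 0.62 and f = 10% gives 0.64.

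False-success rate at 60% true adherence:

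| f (share of non-adherent patients) | First reading | Second reading |
|---|---|---|
| 0 | 3.5% | 3.5% |
| 2% | 4.2% | 4.4% |
| 4% | 4.9% | 5.4% |
| 5% | 5.2% | 6.0% |
| 10% | 6.9% | 9.7% |

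The first reading crosses 5% at f of about 4.4%. The second crosses between 2% and 4%.

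**6. Losses in both groups, first reading.** Let adherent patients also leave, each with probability g. With f = 10% and g = 5%, false success is 4.96%. With f = g = 10% it is 3.5%.

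**7. All 40 kept, missing weeks scored non-adherent.** The rule is 30 of 40, with alpha 3.5% and power 83.9%. If an assumed 2% of would-be adherent patients stop for unrelated reasons and score non-adherent, the rate is 0.8 × 0.98 = 0.784 and power is 76.8%. At 5% it is 0.8 × 0.95 = 0.76 and power is 64.1%.

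**The case against.** The strongest reply is that the inflation is assumed. A strict 7.3 also removes adherent patients, as the example of 8 good weeks in 10 shows, and step 6 shows that mixed losses can leave the error below 5%. This stands, and it limits the claim to losses that fall mainly on non-adherent patients. It does not settle which denominator applies.

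Section 4.5.2 does pull towards keeping withdrawn patients. But it does not say how to score them, and it does not cover a patient who stays in the study and stops logging.

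The reversal at 29 patients also sits on a step of the exact test: the required count drops from 30 to 29 at n = 39 and is still 29 at n = 38. It shows that a reversal is possible, not that one is likely. Section 7.2 also calls for a 95% exact interval, so the p-value is not the only result.

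The stakes are bounded too. The Study Summary moves on to the second phase without an adherence condition, and 8.4 plans no formal interim analysis for stopping. A reader might infer that a wrong Phase 1 result would wrongly open Phase 2; the documents do not make Phase 2 depend on it.

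A reader might also infer that item 6 of 4.5.1, "6. Non-compliance", lets investigators remove patients who are failing the endpoint. The text does not support that. Item 6 is a discretionary right. Section 5.6 does describe compliance ("Patients will have to maintain a weekly 25% reduction of caloric intake for 80% of the logged events in order to be considered compliant"), but as a share of all logged events, and it is not linked to withdrawal. The stated response to diaries in 5.5 is that "these food journals will be collected weekly and modifications will be suggested accordingly".

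**Conclusion.** The conflict between 7.3 and 3.2 is real and concerns the primary feasibility endpoint. The plan does not fix the Phase 1 denominator or say how early leavers score.

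At 60% true adherence, if 5% or 10% of non-adherent patients are affected, false success rises from 3.5% to 5.2% or 6.9% on the first reading and to 6.0% or 9.7% on the second. These figures rest on assumed rates and on losses confined to non-adherent patients. Similar losses among adherent patients remove most or all of the inflation.

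Two stronger inferences should be resisted. One is that the trial will overstate adherence: the documents give no loss rate for either group, so only the possibility is shown. The opposite one is that the second reading is safe because it keeps patients in: early leavers with clean diaries make it no safer than the first. The change should be made; confidence is medium because the size depends on unstated rates.

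**What to change.** In 7.3, add for the adherence endpoint:
- All 40 enrolled Phase 1 patients are analysed.
- Each patient's denominator is her planned number of diet weeks (at least 10), fixed in advance and not shortened by withdrawal.
- Every planned week with fewer than 4 diaries is non-adherent, including weeks after withdrawal for any reason.
- The present 7.3 set is reported as a sensitivity analysis.

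Section 3.2 should say that logged events are these planned weeks. No change to 4.5.1 is needed, because the rule covers every withdrawal whatever its reason.

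The cost is a few sentences and no new data collection. The 30-of-40 rule stays, with alpha 3.5% and power 83.9%. The downside is that a patient who would have adhered but stops for an unrelated reason may count as non-adherent. Power at 80% then falls to 76.8% or 64.1% if this affects an assumed 2% or 5% of would-be adherent patients, so the sensitivity analysis is worth keeping.
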